6.2.2 Non-Amgen Investigational Product: Pembrolizumab

The non-Amgen investigational product pembrolizumab will also be used in this study.

The investigator shall take responsibility for and shall take all steps to maintain appropriate records and ensure appropriate supply, storage, handling, distribution and

usage of trial treatments in accordance with the protocol and any applicable laws and regulations.

Additional details regarding the product(s) are provided in the IPIM.

6.2.2.1 Pembrolizumab Dosage, Administration, and Schedule

Trial treatment should begin as close as possible to the date on which the subject is allocated/assigned. The pembrolizumab treatment to be used in this trial is outlined below in [Table 6-2](#).

Schedule of pembrolizumab dosing and related assessments for cohort Ia are provided in [Table 7-1](#) and [Table 7-2](#), and for cohorts IIa and IIIa are provided in [Table 7-3](#) and [Table 7-4](#). Pembrolizumab will be administered as a dose of 200 mg using a 30-minute IV infusion. Sites should make every effort to target infusion timing to be as close to 30 minutes as possible. However, given the variability of infusion pumps from site to site, a window between - 5 minutes and + 10 minutes is permitted (ie, infusion time is 30 minutes - 5 minutes/+ 10 minutes).

For this trial, an overdose of pembrolizumab will be defined as ≥ 1000 mg (5 times the dose) of pembrolizumab. No specific information is available on the treatment of overdose of pembrolizumab. In the event of overdose of pembrolizumab, the subject should be observed closely for signs of toxicity. Appropriate supportive treatment should be provided if clinically indicated.

Table 6-2. Trial Treatment

Drug	Dose/ Potency	Dose Frequency	Maximum Length of Dosing	Route of Administration	Regimen ^a	Use
Pembrolizumab	200 mg	Every 21 days	Up to 35 cycles	Intravenous	First dose starting at study day 15 (cohort Ia), and study day 19 (cohorts IIa and IIIa) (21-day cycles)	Experimental

^a Starting from pembrolizumab cycle 2, pembrolizumab may be administered ± 3 days from the planned dosing day.

6.2.2.2 Dosage Adjustments, Delays, Rules for Withholding or Restarting, Permanent Discontinuation for Pembrolizumab

6.2.2.2.1 Dose modification of Pembrolizumab if Blinatumomab has been interrupted

If toxicities due to blinatumomab do not resolve to grade ≤ 1 within 7 days of treatment interruption and supportive care as outlined, pembrolizumab will also be interrupted until both may be resumed per protocol.

The first dose of pembrolizumab must be delayed if blinatumomab is interrupted during the step dose period per protocol (see [Table 6-1](#)). The first dose of pembrolizumab can only be given after the blinatumomab target dose is reached (+ 4 days); also, before adding pembrolizumab, there should be no blinatumomab dose interruption due to adverse events, no $>$ grade 1 CRS and/or neurologic events.

6.2.2.2.2 Dose Modification and Toxicity Management for Immune-related Adverse Events Associated With Pembrolizumab

Adverse events associated with pembrolizumab exposure may represent an immune-related response. These immune-related adverse events (irAEs) may occur shortly after the first dose or several months after the last dose of pembrolizumab treatment and may affect more than one body system simultaneously. Therefore, early recognition and initiation of treatment is critical to reduce complications. Based on existing clinical study data, most irAEs were reversible and could be managed with interruptions of pembrolizumab, administration of corticosteroids, and/or other supportive care. For suspected irAEs ensure adequate evaluation to confirm etiology or exclude other causes. Additional procedures or tests such as bronchoscopy, endoscopy, skin biopsy may be included as part of the evaluation. Dose modification and toxicity management guidelines for irAEs associated with pembrolizumab are provided in [Table 6-3](#).

Table 6-3. Dose Modification and Toxicity Management Guidelines for Immune-related Adverse Events Associated With Pembrolizumab

General instructions:				
1. Severe and life-threatening irAEs should be treated with IV corticosteroids followed by oral steroids. Other immunosuppressive treatment should begin if the irAEs are not controlled by corticosteroids. 2. Pembrolizumab must be permanently discontinued if the irAE does not resolve or the corticosteroid dose is not \leq 10 mg/day within 12 weeks of the last pembrolizumab treatment. 3. The corticosteroid taper should begin when the irAE is \leq Grade 1 and continue at least 4 weeks. 4. If pembrolizumab has been withheld, pembrolizumab may resume after the irAE decreased to \leq Grade 1 after corticosteroid taper.				
irAEs	Toxicity grade (CTCAE v4.0)	Action with pembrolizumab	Corticosteroid and/or other therapies	Monitoring and follow-up
Pneumonitis	Grade 2	Withhold	
 Administer corticosteroids (initial dose of 1 to 2 mg/kg prednisone or equivalent) followed by taper Add prophylactic antibiotics for opportunistic infections 	
 Monitor participants for signs and symptoms of pneumonitis Evaluate participants with suspected pneumonitis with radiographic imaging and initiate corticosteroid treatment
	Recurrent Grade 2, Grade 3 or 4	Permanently discontinue		
Diarrhea / Colitis	Grade 2 or 3	Withhold	
 Administer corticosteroids (initial dose of 1 to 2 mg/kg prednisone or equivalent) followed by taper 	
 Monitor participants for signs and symptoms of enterocolitis (ie, diarrhea, abdominal pain, blood or mucus in stool with or without fever) and of bowel perforation (ie, peritoneal signs and ileus). Participants with \geq Grade 2 diarrhea suspecting colitis should consider GI consultation and performing endoscopy to rule out colitis. Participants with diarrhea/colitis should be advised to drink liberal quantities of clear fluids. If sufficient oral fluid intake is not feasible, fluid and electrolytes should be substituted via IV infusion.
	Recurrent Grade 3 or Grade 4	Permanently discontinue		

Footnotes defined on last page table

Table 6-3. Dose Modification and Toxicity Management Guidelines for Immune-related Adverse Events Associated With Pembrolizumab

General instructions:				
1. Severe and life-threatening irAEs should be treated with IV corticosteroids followed by oral steroids. Other immunosuppressive treatment should begin if the irAEs are not controlled by corticosteroids. 2. Pembrolizumab must be permanently discontinued if the irAE does not resolve or the corticosteroid dose is not ≤ 10 mg/day within 12 weeks of the last pembrolizumab treatment. 3. The corticosteroid taper should begin when the irAE is \leq Grade 1 and continue at least 4 weeks. 4. If pembrolizumab has been withheld, pembrolizumab may resume after the irAE decreased to \leq Grade 1 after corticosteroid taper.				
irAEs	Toxicity grade (CTCAE v4.0)	Action with pembrolizumab	Corticosteroid and/or other therapies	Monitoring and follow-up
AST or ALT elevation or Increased Bilirubin	Grade 2 ^a	Withhold	
 Administer corticosteroids (initial dose of 0.5 to 1 mg/kg prednisone or equivalent) followed by taper 	
 Monitor with liver function tests (consider weekly or more frequently until liver enzyme value returned to baseline or is stable)
	Grade 3 ^b or 4 ^c	Permanently discontinue	
 Administer corticosteroids (initial dose of 1 to 2 mg/kg prednisone or equivalent) followed by taper 	
Type 1 diabetes mellitus (T1DM) or Hyperglycemia	New onset T1DM or Grade 3 or 4 hyperglycemia associated with evidence of β -cell failure	Withhold ^d	
 Initiate insulin replacement therapy for participants with T1DM Administer anti-hyperglycemic in participants with hyperglycemia 	
 Monitor participants for hyperglycemia or other signs and symptoms of diabetes.
Hypophysitis	Grade 2	Withhold	
 Administer corticosteroids and initiate hormonal replacements as clinically indicated. 	
 Monitor for signs and symptoms of hypophysitis (including hypopituitarism and adrenal insufficiency)
	Grade 3 or 4	Withhold or permanently discontinue ^d		

Footnotes defined on last page table

Table 6-3. Dose Modification and Toxicity Management Guidelines for Immune-related Adverse Events Associated With Pembrolizumab

General instructions:				
1. Severe and life-threatening irAEs should be treated with IV corticosteroids followed by oral steroids. Other immunosuppressive treatment should begin if the irAEs are not controlled by corticosteroids. 2. Pembrolizumab must be permanently discontinued if the irAE does not resolve or the corticosteroid dose is not ≤ 10 mg/day within 12 weeks of the last pembrolizumab treatment. 3. The corticosteroid taper should begin when the irAE is \leq Grade 1 and continue at least 4 weeks. 4. If pembrolizumab has been withheld, pembrolizumab may resume after the irAE decreased to \leq Grade 1 after corticosteroid taper.				
irAEs	Toxicity grade (CTCAE v4.0)	Action with pembrolizumab	Corticosteroid and/or other therapies	Monitoring and follow-up
Hyperthyroidism	Grade 2	Continue	
 Treat with non-selective beta-blockers (eg, propranolol) or thionamides as appropriate 	
 Monitor for signs and symptoms of thyroid disorders.
	Grade 3 or 4	Withhold or permanently discontinue ^d		
Hypothyroidism	Grade 2, 3, 4	Continue	
 Initiate thyroid replacement hormones (eg, levothyroxine or liothyronine) per standard of care 	
 Monitor for signs and symptoms of thyroid disorders.
Nephritis: grading according to increased creatinine or acute kidney injury	Grade 2	Withhold	
 Administer corticosteroids (prednisone 1 to 2 mg/kg or equivalent) followed by taper. 	
 Monitor changes of renal function
	Grade 3 or 4	Permanently discontinue		
Neurological Toxicities	Grade 2	Withhold	
 Based on severity of AE administer corticosteroids 	
 Ensure adequate evaluation to confirm etiology and/or exclude other causes
	Grade 3 or 4	Permanently discontinue		
Myocarditis	Grade 1	Withhold	
 Based on severity of AE administer corticosteroids 	
 Ensure adequate evaluation to confirm etiology and/or exclude other causes
	Grade 2, 3 or 4	Permanently discontinue		

Footnotes defined on last page table

Table 6-3. Dose Modification and Toxicity Management Guidelines for Immune-related Adverse Events Associated With Pembrolizumab

General instructions:				
1. Severe and life-threatening irAEs should be treated with IV corticosteroids followed by oral steroids. Other immunosuppressive treatment should begin if the irAEs are not controlled by corticosteroids. 2. Pembrolizumab must be permanently discontinued if the irAE does not resolve or the corticosteroid dose is not ≤ 10 mg/day within 12 weeks of the last pembrolizumab treatment. 3. The corticosteroid taper should begin when the irAE is \leq Grade 1 and continue at least 4 weeks. 4. If pembrolizumab has been withheld, pembrolizumab may resume after the irAE decreased to \leq Grade 1 after corticosteroid taper.				
irAEs	Toxicity grade (CTCAE v4.0)	Action with pembrolizumab	Corticosteroid and/or other therapies	Monitoring and follow-up
Exfoliative Dermatologic Conditions	Suspected SJS, TEN, or DRESS	Withhold	
 Based on severity of AE administer corticosteroids 	
 Ensure adequate evaluation to confirm etiology or exclude other causes
	Confirmed SJS, TEN, or DRESS	Permanently discontinue		
All Other immune-related AEs	Persistent Grade 2	Withhold	
 Based on severity of AE administer corticosteroids 	
 Ensure adequate evaluation to confirm etiology or exclude other causes
	Grade 3	Withhold or discontinue based on the event ^e		
	Recurrent Grade 3 or Grade 4	Permanently discontinue		

Page 4 of 4

AE = adverse event; ALT = alanine aminotransferase; AST = aspartate aminotransferase; CTCAE = Common Terminology Criteria for Adverse Events; **DRESS = Drug Rash with Eosinophilia and Systemic Symptom**; GI = gastrointestinal; **IO = immuno-oncology**; **ir = immune related**; irAE = immune-related adverse event; IV = intravenous; **SJS = Stevens-Johnson Syndrome**; **T1DM = type 1 diabetes mellitus**; **TEN=Toxic Epidermal Necrolysis**; ULN = upper limit of normal

Note: Non-irAE will be managed as appropriate, following clinical practice recommendations.

^a AST/ALT: $> 3.0 - 5.0 \times$ ULN, if baseline normal; $> 3.0 - 5.0 \times$ baseline, if baseline abnormal; bilirubin: $> 1.5 - 3.0 \times$ ULN, if baseline normal; > 1.5 to $3.0 \times$ baseline, if baseline abnormal

^b AST/ALT: > 5.0 to $20.0 \times$ ULN, if baseline normal; $> 5.0 - 20.0 \times$ baseline, if baseline abnormal; bilirubin: $> 3.0 - 10.0 \times$ ULN, if baseline normal; $> 3.0-10.0 \times$ baseline, if baseline abnormal

^c AST/ALT: $> 20.0 \times$ ULN, if baseline normal; $> 20.0 \times$ baseline, if baseline abnormal; bilirubin: $> 10.0 \times$ ULN if baseline normal; $> 10.0 \times$ baseline if baseline abnormal

^d The decision to withhold or permanently discontinue pembrolizumab is at the discretion of the investigator or treating physician. If control achieved or \leq Grade 2, pembrolizumab may be resumed.

^e Events that require discontinuation include but are not limited to: **encephalitis and other clinically important irAEs (eg vasculitis and sclerosing cholangitis)**.

6.2.3 Dosage Adjustments, Delays, Rules for Withholding or Restarting, Permanent Discontinuation of Protocol Specified Therapy

Treatment with protocol specified therapy should be discontinued in the event of any of the following:

- Documented disease progression **or relapse** per the Lugano Classification (Cheson et al, 2014) and Revised Response Criteria (Cheson et al, 2007) at any time following the first (8 week) cycle of blinatumomab.

After the first documentation of progression **or relapse**, it is at the discretion of the investigator to keep a clinically stable subject on trial treatment or to stop trial treatment until repeat imaging performed 4 to 8 weeks from initial assessment suspicious for PD **or relapse** for subjects meeting criteria in Section 7.3.12. The first documented progression **or relapse** will still be counted as a progression/**relapse** event.

- Occurrence of an adverse event which makes discontinuation from treatment necessary due to protocol-specified safety criteria or desirable in the investigator's and/or the subjects opinion
- Investigator's decision that a change of therapy is in the subject's best interest
- Administration of relevant non-permitted concomitant medications
- Investigator's decision that a subject does not benefit from treatment anymore, eg, non-response or development of progressive disease
- Intercurrent medical condition, which in the opinion of the investigator or the subject precludes further treatment of the subject
- Withdrawal of subject's consent to study treatment

6.3 Dexamethasone Premedication

Mandatory premedication with dexamethasone is required. Refer to [Table 6-4](#) for details.

Table 6-4. Dexamethasone Predose Treatment and for Events

Treatment Phase	Target Subjects:	Dexamethasone Dose
Pre-dose Dexamethasone Prior to Each Blinatumomab Treatment Cycle and Before Each Dose Step Increase	All subjects	Dexamethasone 20 mg IV: within 6 hours prior to start of treatment in each treatment cycle, and within 6 hours prior to dose step (increase).
Infusion Interruption/Dose Modification Due to Adverse Event or Interruption due to Technical/Logistical Event	Subjects who interrupt treatment > 4 hours	Dexamethasone 20 mg IV: within 6 hours prior to re-start of treatment
In case of signs of CRS	Subjects with signs of CRS	Dexamethasone orally or IV at a dose maximum of 3 doses of 8 mg/day (24 mg/day) for up to 72 hours. The dose should then be reduced step-wise over 4 days.
Infusion Interruption/Dose Modification Due to Neurologic Events	Subjects with neurologic event	Dexamethasone should be administered at a dose of at least 24 mg/day for up to 72 hours. Dexamethasone will then be reduced step-wise over 4 days.

CRS = cytokine release syndrome; IV = intravenous

6.4 Hepatotoxicity Stopping and Rechallenge Rules

Subjects with abnormal hepatic laboratory values (ie, alkaline phosphatase [ALP], aspartate aminotransferase [AST], alanine aminotransferase [ALT], total bilirubin [TBL]) and/or international normalized ratio [INR] and/or signs/symptoms of hepatitis (as described below) may meet the criteria for withholding or permanent discontinuation of Amgen investigational product or other protocol-required therapies as specified in the Guidance for Industry Drug-Induced Liver Injury: Premarketing Clinical Evaluation, July 2009.

6.4.1 Criteria for Withholding and/or Permanent Discontinuation of Blinatumomab and Other Protocol-required Therapies Due to Potential Hepatotoxicity

The following stopping and/or withholding rules apply to subjects for whom another cause of their changes in liver biomarkers (TBL, INR and transaminases) has not been identified.

Important alternative causes for elevated AST/ALT and/or TBL values include, but are not limited to:

- Hepatobiliary tract disease
- Viral hepatitis (eg, Hepatitis A/B/C/D/E, Epstein-Barr Virus, cytomegalovirus, Herpes Simplex Virus, Varicella, toxoplasmosis, and Parvovirus)
- Right sided heart failure, hypotension or any other cause of hypoxia, congestion, and/or ischemia to the liver.
- Exposure to hepatotoxic agents/drugs or hepatotoxins, including herbal and dietary supplements, plants and mushrooms
- Heritable disorders causing impaired glucuronidation (eg, Gilbert's Syndrome, Crigler-Najjar syndrome) and drugs that inhibit bilirubin glucuronidation (eg, indinavir, atazanavir)
- Alpha-one antitrypsin deficiency
- Alcoholic hepatitis
- Autoimmune hepatitis
- Wilson's disease and hemochromatosis
- Nonalcoholic Fatty Liver Disease including Steatohepatitis (NASH)
- Non-hepatic causes (eg, rhabdomyolysis, hemolysis)
- Cytokine release syndrome

If investigational product(s) is/are withheld, the subject is to be followed according to recommendations in [Appendix A](#) for possible drug-induced liver injury (DILI).

Rechallenge may be considered if an alternative cause for impaired liver tests (ALT, AST, ALP) and/or elevated TBL, is discovered and the laboratory abnormalities resolve to normal or baseline (Section [6.4.2](#)).

Refer to [Table 6-3](#) for pembrolizumab dose modifications.

Table 6-5. Conditions for Withholding and/or Permanent Discontinuation of Blinatumomab Due to Potential Hepatotoxicity

Analyte	Temporary Withholding	Permanent Discontinuation
TBL	> 3x upper limit of normal (ULN) at any time	> 2x ULN
		OR
INR	--	> 1.5 (for subjects not on anticoagulation therapy)
	OR	AND
AST/ALT	> 8x ULN at any time > 5x ULN but < 8x ULN for ≥ 14 days > 3x ULN with clinical signs or symptoms that are consistent with hepatitis (such as right upper quadrant pain/tenderness, fever, nausea, vomiting, jaundice).	No other cause for the combination of the above laboratory abnormalities is immediately apparent > 3x ULN (when baseline was < ULN)
	OR	
ALP	> 8x ULN at any time	--

ALP = alkaline phosphatase; ALT = alkaline aminotransferase; AST = aspartate aminotransferase; INR = international normalized ratio; TBL = total bilirubin

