4.1 Inclusion Criteria

In order to be eligible for participation in this trial, the subject must meet the following criteria:

101. Subject/legally acceptable representative has provided written informed consent prior to initiation of any study-specific procedures.
102. Age \geq 18 years at the time of informed consent
103. Have histologically confirmed DLBCL that is either:
 - Refractory after at least 1 regimen of systemic chemotherapy and/or targeted therapy, and refractory is defined as progressive or stable disease as the best response to the most recent systemic chemotherapy regimen or disease progression or relapse within 12 months after autologous stem cell transplantation; when using PET for assessment, for subjects with refractory disease and who have received radiotherapy, PET positivity should be demonstrated no less than 6 weeks after the last dose of radiotherapy (Crump et al, 2017; Neelapu et al, 2017; Cheson et al, 2007), or
 - In first or later relapse if have received at least 2 systemic regimens since time of diagnosis, or
 - Relapsed post-autologous or allogeneic HSCT with adequate organ function after proximity to transplantation time exclusions as specified in Exclusion Criteria 208 and 209
104. Have measurable disease defined as at least 1 lesion that can be accurately measured in at least 2 dimensions with spiral computed tomography (CT) scan. Minimum measurement must be either $>$ 15 mm in the longest diameter OR $>$ 10 mm in the short axis.
105. Demonstrate adequate organ function as defined in Table 4-1.

Table 4-1. Adequate Organ Function Laboratory Values

System	Laboratory Value
Hematological	
Absolute neutrophil count (ANC)	≥ 1,500/mcL
Platelets	≥ 100,000/mcL
Hemoglobin	≥ 9 g/dL or ≥ 5.6 mmol/L
Renal	
Creatinine OR Measured or calculated ^a creatinine clearance (CrCl) (glomerular filtration rate (GFR) can also be used in place of creatinine or CrCl)	≤ 1.5xULN OR ≥ 60 mL/min for subject with creatinine levels >1.5 x institutional upper limit of normal (ULN)
Hepatic	
Total bilirubin	≤ 1.5xULN OR Direct bilirubin ≤ ULN for subjects with total bilirubin levels > 1.5 x ULN
AST (SGOT) and ALT (SGPT)	≤ 2.5xULN OR ≤ 5xULN for subjects with liver metastases
Coagulation	

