Elevated Liver Enzymes		
 • Interrupt blinatumomab if any one of the following occurs: 
 ○ TBL > 3 x ULN at any time ○ ALP > 8 x ULN at any time ○ AST or ALT > 8 x ULN at any time ○ AST or ALT > 5 x ULN but < 8 x ULN for ≥ 14 days ○ AST or ALT > 3 x ULN with clinical signs or symptoms that are consistent with hepatitis (eg, right upper quadrant abdominal pain/tenderness, fever, nausea, vomiting, jaundice) • Permanently discontinue blinatumomab if: 
 ○ TBL > 2 x ULN OR INR >1.5 (for subjects not on anticoagulant therapy) 
AND
 
 ○ AST or ALT > 3x ULN (when baseline was <ULN) 
AND
 
 ○ no other cause for the combination of the above laboratory abnormalities is immediately apparent 
 • Refer to Section 6.4 for additional detail
Other Clinically Relevant Adverse Events	3	
 • Interrupt blinatumomab until event improves to grade ≤1 • Restart no less than 72 hours after the initial observation of the grade 3 event at the following dose levels: 
 ○ If event occurred at 56 or 112 µg/day, resume at 28 µg/day ○ If event occurred at 28 µg/day, resume at 9 µg/day • Escalate up 1 dose level after 7 days if toxicity does not reoccur. Increase dose stepwise at 7-day intervals to target dose of cohort (28 µg/day for cohort Ia, 56 µg/day for cohort IIa, 112 µg/day for cohort IIIa) if toxicity does not reoccur. • Permanently discontinue blinatumomab if: 
 ○ Initial grade 3 event does not improve to grade ≤ 1 within 14 days, (with the exception of delay in restart due to logistical difficulties, in which case the restart may be postponed for an additional 7 days) 
OR
 
 ○ Grade 3 event reoccurs at the lower dose level within 7 days of re-initiation, OR ○ Grade 3 event reoccurs at a dose of 9 µg/day without prior step-dose escalation
	4	
 • Permanently discontinue blinatumomab

Page 2 of 2

ALP = alkaline phosphatase; ALT = alanine aminotransferase; AST = aspartate aminotransferase; INR = international normalized ratio; MRI = magnetic resonance imaging; TBL = total bilirubin; ULN = upper limit of normal

^a Obtain brain MRI and perform cerebrospinal fluid (CSF) analysis, if there are no contraindications.

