14. APPENDICES

Appendix A. Additional Safety Assessment Information

Refer to the NCI Common Terminology Criteria for Adverse Events (CTCAE) version 4.0 for adverse event grading and information. The CTCAE scale is available at the following location:

http://ctep.cancer.gov/protocolDevelopment/electronic_applications/ctc.htm

Reporting

To facilitate appropriate monitoring for signals of Drug-induced liver injury (DILI), cases of concurrent aspartate aminotransferase (AST) or alanine aminotransferase (ALT) and total bilirubin (TBL) and/or INR elevation according to the criteria specified in Section 6.4 require the following:

- The event is to be reported to Amgen as a serious adverse event within 24 hours of discovery or notification of the event (ie, before additional etiologic investigations have been concluded)
- The appropriate case report form (CRF) (eg, Event CRF) that captures information necessary to facilitate the evaluation of treatment-emergent liver abnormalities is to be completed and sent to Amgen.

Other events of hepatotoxicity and potential DILI are to be reported as serious adverse events if they meet the criteria for a serious adverse event defined in Section 9.2.2.2.

Additional Clinical Assessments and Observation

All subjects in whom investigational product(s) or protocol-required therapies is/are withheld (either permanently or conditionally) due to potential DILI as specified in Table 6-5 or who experience AST or ALT elevations > 3 x upper limit of normal (ULN) or 2-fold increases above baseline values for subjects with elevated values before drug are to undergo a period of “close observation” until abnormalities return to normal or to the subject’s baseline levels.

Assessments that are to be performed during this period include:

- Repeat AST, ALT, alkaline phosphatase (ALP), bilirubin (total and direct), and INR within 24 hours
- In cases of TBL > 2 x ULN or international normalized ratio (INR) > 1.5 , retesting of liver tests, bilirubin (total and direct), and INR is to be performed every 24 hours until laboratory abnormalities improve

Testing frequency of the above laboratory tests may decrease if the abnormalities stabilize or the investigational product(s) or protocol-required therapies has/have been discontinued AND the subject is asymptomatic.

- Initiate investigation of alternative causes for elevated AST or ALT and/or elevated TBL. The following are to be considered depending on the clinical situation:

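### Tables 6-1 and 6-5 require no blinatumomab hold or stop for asymptomatic, unexplained AST/ALT > 3x to 5x ULN with TBL > 2x to 3x ULN (or INR > 1.5) when baseline AST/ALT was at or above ULN

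*Protocol*

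**What the plan says.** The blinatumomab liver rules are in Protocol Table 6-1 (Section 6.2.1.4.1) and Table 6-5 (Section 6.4.1). Both require permanent discontinuation when three things coincide: TBL > 2x ULN, or INR > 1.5 in a subject not on anticoagulation; a transaminase elevation; and no other evident cause. The transaminase limb is "> 3x ULN (when baseline was < ULN" in Table 6-5 and "AST or ALT > 3x ULN (when baseline was <ULN" in Table 6-1 (closing brackets omitted). The two tables agree, so the restriction is not an extraction fault.

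Protocol Table 4-1 (Section 4.1) admits AST/ALT up to 2.5x ULN, or "≤ 5xULN for subjects with liver metastases". Neither liver table has a line for subjects who enter at or above ULN.

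The temporary holds do not depend on baseline. They need TBL > 3x ULN, ALP > 8x, AST/ALT > 8x, AST/ALT between 5x and 8x for at least 14 days, or AST/ALT > 3x with signs or symptoms of hepatitis (fever and jaundice are listed). For other clinically relevant grade 3 events, Table 6-1 says "Interrupt blinatumomab until event improves to grade ≤1".

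Protocol Appendix A requires close observation for AST/ALT > 3x ULN or for "2-fold increases above baseline values for subjects with elevated values before drug". Once TBL is > 2x ULN or INR is > 1.5, "retesting of liver tests, bilirubin (total and direct), and INR is to be performed every 24 hours until laboratory abnormalities improve".

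**The concern.** Rising transaminases with rising bilirubin or INR and no explanation is the pattern the combined rule exists to catch. Limiting the rule to baseline < ULN is reasonable in itself: a subject with liver metastases may enter at up to 5x ULN and would meet an unqualified > 3x limb on day 1. What is missing is the substitute for everyone else whose baseline is at or above ULN. Two subjects with identical on-study values can therefore face opposite instructions because of a small baseline difference. One must stop permanently. The other may stay on continuous infusion while laboratory tests are repeated.

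Two related protections refer to the same criteria and, read literally, also miss these subjects. The bar on any rechallenge (Section 6.4.2) refers to Table 6-5. The automatic SAE report for combined liver elevations in Appendix A applies to cases "according to the criteria specified in Section 6.4 require the following".

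**Working it through.** The plan prints no figure to reproduce. The check applies each mandatory blinatumomab rule to the band in question.

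**Inputs.** Stop and hold limits: Tables 6-1 and 6-5. Grade 4 rule: Section 6.2.1.4.1. Baseline limits: Table 4-1. Grades: SAP Appendix B, where AST/ALT > 3x to 5x ULN is grade 2 and > 5x is at least grade 3; bilirubin > 1.5x to 3x is grade 2 and > 3x is at least grade 3. The documents print no INR grade cut-offs, so INR values are assumed to lie below a clinically relevant grade 3 event.

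**Step 1. Each rule against the band** (AST/ALT > 3x to 5x, TBL > 2x to 3x, ALP not above 8x, no symptoms, no other cause, baseline ≥ ULN):

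| Rule | Needs | Met? |
|---|---|---|
| Combined permanent stop | baseline < ULN | no |
| TBL hold | TBL > 3x | no |
| ALP hold | ALP > 8x | no |
| AST/ALT hold | > 8x, or 5x to 8x for ≥ 14 days | no |
| Symptom hold | > 3x with hepatitis signs or symptoms | no |
| Other clinically relevant event | grade 3 or 4 | no (grade 2 and grade 2) |
| General rule | grade 4, possibly related | no |

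**Step 2. Grid.** With AST 3.1x, 4x or 5x ULN, and TBL 2.1x or 3.0x (or INR 1.6 or 2.4), baseline < ULN gives a permanent stop in every cell and baseline ≥ ULN gives no mandatory action in any cell. The gap closes at TBL 3.1x (hold), at AST 5.1x (grade 3 hold if judged clinically relevant), or when hepatitis signs or symptoms are present (hold).

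**Step 3. Two cases**, no symptoms, no other cause, ALP 1.5x ULN, baseline TBL normal.

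- Case A: AST 4x, TBL 2.2x ULN. Baseline AST 0.95x: permanent stop. Baseline 1.05x to 2.5x: no required hold or stop. Retesting every 24 hours applies. The event is an event of clinical interest (ECI) with a 24-hour report under Section 9.1.4 (AST ≥ 3x, TBL ≥ 2x, ALP < 2x). At ALP 2.5x the ECI report drops out.
- Case B: AST 4x, TBL 1.2x ULN, INR 1.6, no anticoagulant. Baseline 0.95x: permanent stop. Baseline 1.05x: no required hold or stop, and not an ECI because TBL is < 2x. Retesting every 24 hours applies.

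Table 6-3 withholds pembrolizumab at grade 2 if the event is judged immune-related, but does not govern blinatumomab. In case A the bilirubin limb meets it. In case B the AST limb does so for an abnormal baseline only when 4/baseline > 3, that is, baseline < 4/3 = 1.33x ULN (4/1.05 = 3.8; 4/1.5 = 2.7).

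**Step 4. How much of the band a 2x-baseline line would reach.** Its threshold is max(3, 2 × baseline), so the share of the AST interval from 3x to 5x covered is (5 − max(3, 2 × baseline))/2.

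| Baseline AST (x ULN) | Threshold | Share covered |
|---|---|---|
| up to 1.5 | 3.0 | (5 − 3)/2 = 100% |
| 1.75 | 3.5 | (5 − 3.5)/2 = 75% |
| 2.0 | 4.0 | (5 − 4)/2 = 50% |
| 2.25 | 4.5 | (5 − 4.5)/2 = 25% |
| 2.5 | 5.0 | only AST of exactly 5x |

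Above 2.5x, none of the band is covered. These are widths of a laboratory interval, not shares of patients.

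**The case against.** The strongest reply is that the remaining corner is narrow and watched. It must be asymptomatic, and fever is a listed hepatitis sign while Section 2.1 names pyrexia among the commonest events in the earlier phase 2 blinatumomab study. It must also be unexplained, and a subject with abnormal baseline liver tests may have a candidate cause. Inside it, Appendix A requires daily retesting and a search for causes, although testing may be reduced once values stabilise in an asymptomatic subject. Section 6.2.1.4.1 lets the investigator interrupt or stop, Section 6.2.3 calls for discontinuation where the investigator or subject thinks it desirable, and Section 8.2 lets the sponsor withdraw the subject from treatment. If serious criteria are met, an SAE report follows: "Other events of hepatotoxicity and potential DILI are to be reported as serious adverse events if they meet the criteria". Section 9.1.3 names drug-induced liver injury as an example. Restart after a hepatic hold is already restricted by Sections 6.4.1 and 6.4.2. All of this stands and limits the weight of the point. None of it makes a hold mandatory.

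Section 6.4 also cites an external liver-injury guidance that cannot be consulted here. A reader might infer that nothing at all governs these subjects; the documents do not support that. They do show that the tables sites act on contain no raised-baseline line.

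Any cut-off creates neighbours treated differently. Under a 2x-baseline line at AST 4x ULN, baseline 2.0x is caught (4/2.0 = 2.0) and 2.05x is not (4/2.05 = 1.95). That is fair, but here the whole raised-baseline group lacks a rule, which is more than a threshold effect.

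A reader might also conclude that the permanent stop itself should extend to raised baselines at 2x baseline. Appendix A uses that multiple only to trigger observation, so it supports an interruption better than an irreversible stop.

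**Conclusion.** The gap is real and confined to one band: baseline AST/ALT ≥ ULN, no hepatitis signs or symptoms, no other cause, AST/ALT > 3x to 5x ULN, with TBL > 2x to 3x ULN or INR > 1.5 off anticoagulation. The upper edge of the INR route cannot be stated from the documents.

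Two stronger readings should be resisted. One is that subjects with a raised baseline have no liver stopping rules; every temporary hold, and the grade 3 and grade 4 rules, apply to them. The other is that the baseline qualifier is a mistake to be deleted; some qualifier is needed because of the liver-metastasis allowance.

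The number affected is not given. SAP Section 11 says Part 2 will not proceed, so reach is at most 30 Part 1 subjects, and only while they receive blinatumomab (8 weeks plus an optional 28 days). The documents do not show that anyone with a raised baseline is still on it. The conclusion assumes that the qualifier refers to the baseline of the transaminase that rises and that grading follows SAP Appendix B. This is a safety wording gap of low to moderate priority.

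**What to change.** Keep the permanent-stop line for baseline < ULN. Add one line to Tables 6-1 and 6-5 for baseline AST/ALT ≥ ULN: if AST/ALT is > 3x ULN and at least 2x the subject's baseline, with TBL > 2x ULN or INR > 1.5 (not on anticoagulation) and no other cause immediately apparent, interrupt blinatumomab, start the Appendix A work-up and submit the SAE report. Allow restart only under the conditions already in Sections 6.4.1 and 6.4.2: an alternative cause is found, values return to normal or baseline, and subject, investigator and sponsor agree unanimously. Otherwise discontinue permanently. State in Appendix A that its automatic SAE trigger includes this line. The sponsor's hepatic safety team should confirm the 2x multiple as a dosing threshold.

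The cost is one line in two tables and a cross-reference, with no new tests, no extra subjects and no SAP change. The downside is a few more interruptions in subjects with abnormal baselines, some of whom might have tolerated continued infusion. Cover is partial: complete up to baseline 1.5x ULN, half the AST interval at 2.0x, and almost nothing from about 2.5x upward, where observation and discretion remain the safeguards.
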